- H1 Metabolic phenotypes based on basic mechanisms of adipose tissue are associated to the cardiovascular risk modification after bariatric surgery.
- H0. Metabolic phenotypes based on basic mechanisms of adipose tissue are NOT associated to the cardiovascular risk modification after bariatric surgery.

GENERAL OBJETIVE

To evaluate the association of the cardiovascular benefit of the obese patient after bariatric surgery with the basic mechanisms of adipose tissue (metabolic profile)

SPECIFIC OBJECTIVES

- Characterize the basal (pre-surgical) metabolic profile of adipose tissue.
- Evaluate post-surgical modification of cardiovascular prognosis
- Determine the association of the cardiovascular prognosis modification (risk subgroups) with the basal metabolic profile.

DESIGN

This is an OBSERVATIONAL study, of a prospective cohort follow-up. We will study morbidly obese patients who undergo bariatric surgery (this is not a proposal of the present protocol, it is routinely done as a treatment for morbid obesity in the CMN "20 de Noviembre", ISSSTE, and it would also be carried out although the patient does not participate in this study). It was considered that the independent variable is the change in cardiovascular risk after bariatric surgery and the dependent variable is the basal metabolic profile of adipose tissue. This order of variables was decided by methodological strategy, since it will be more convenient to determine and stratify based on the change in cardiovascular risk, than based on the basal metabolic profile of adipose tissue.

$$n = \frac{(Z^{\alpha/2})^2 (p(1-p))}{d^2}$$

where:

n = sample size.

$Z^{\alpha/2} = Z$

value of the alpha error with a confidence of 95%, assigning alpha = 0.05

p =

Expected population prevalence for the event under study (according to previous reports).

d

=difference between the expected population prevalence value and the acceptable error. Considering the average difference in the modification of the basic mechanisms in adipose tissue associated with metabolic risk in similar studies

$$\begin{array}{ll}
 (1.96)^2 (0.20 (1-0.20)) & 0.614 \\
 n = \frac{\text{_____}}{(0.13)^2} & n = \frac{\text{_____}}{0.0169} = 36.3
 \end{array}$$

Additionally, for reasons of comparison and standardization of results, a C group would be considered: 10 non-obese patients undergoing non-bariatric surgery.

Definition of the observation units.

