Prior signature of informed consent, will include patients with morbid obesity, candidates for bariatric surgery and without additional modifiers of adipose tissue metabolism. Patients will be chosen in accordance with the criteria of the Bariatric Surgery Service, without modifying the routine procedures performed in this service.

At the same time, a group of non-obese patients (obesity comparison group) scheduled and undergoing non-bariatric abdominal surgery (hernioplasty, cholecystectomy, appendectomy, etc.) will be included. In all groups, total body fat, subcutaneous and visceral fat will be determined non-invasively by computed tomography, with the support of the Department of Imaging ([name] and [name]) as described below:

TOMOGRAPHIC MEASUREMENT OF SUBCUTANEOUS AND VISCERAL GREASE

Subcutaneous fat:

The thickness of adipose tissue will be measured, in the abdominal thickest site, at the level of the umbilical scar, with references from the skin to the muscular layer, either in vertical measurement (antero-posterior) or in lateral measurement.

Visceral fat:

Epicardial fat: The thickness of the adipose tissue will be measured epicardial level, in the thickest site.

Preperitoneal fat:

The thickness of adipose tissue will be measured, level of the umbilical scar; from the muscular layer (vertical measurement or ant-post) to the first visceral structure.

Perirenal fat:

The thickness of adipose tissue will be measured perirenal, in the thickest site.

During the surgical act, a sample of 1-2 cubic cm of visceral and subcutaneous adipose tissue will be taken, in all groups, considering all aspects of patient Ethics and Biosafety described in the respective sections of this project. In patients with laboratorial evidence and image of progression to NAFLD, a sample of 1-2 cubic cm of liver tissue will be taken, in accordance with international guidelines for diagnosis and treatment, and with the study protocol established by the service. It will be guaranteed that the taking of biopsies will not affect the course of the surgery. The biological samples acquired will be properly identified, contained and stored for a maximum period of 1 year. Analysis and determinations will be made according to good laboratory practices. Subsequently, they will be treated and disposed of in appropriate bags for disposal. To comply with the provisions of section 6 of NOM-087-ECOL-SSA1-2002 Biological-Infectious Waste.

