To study the characteristics of each metabolic profile, the following variables will be analyzed:

- a) Adipose tissue (visceral and subcutaneous) where the degree of differentiation and hypertrophy of adipocytes and angiogenesis will be determined by morphometric methods of histopathology; as well as markers of inflammation, oxidative stress, endoplasmic reticulum stress and adipose tissue dysfunction through immunohistochemistry and in vitro tests on isolated adipocytes.
- b) Liver tissue the degree of steatosis, steatohepatitis and fibrogenesis, considered as clinical progression of metabolic damage, will be determined.
- c) Serum level, inflammation markers (TNFa, CRP and IL-6) and adipokines (leptin, adiponectin, resistin) will be determined by ELISA.

Finally, in all groups, follow-up variables related to post-surgical modification of cardiovascular risk will be determined; through:

Prognostic scales of cardiovascular mortality: They will be determined by Drs. [name] and [name], based on probability calculation with variables such as age, gender, co-morbidities, etc. using Framingham or SCORE scales. Place: Clinical Research Division, CMN "November 20", ISSSTE.

Determination of serum markers of endothelial dysfunction and ankle / arm index. They will be determined by [name] [name] and associated researchers, using commercially available ELISA kits and direct determination of systolic pressure in the ankle and arm, with the help of Doppler scan type Doptone, respectively. Place: Biomedical Research Laboratory and Clinical Research Division, CMN "November 20", ISSSTE.

Determination of subclinical atherogenesis (thickness of the carotid intima media). It will be determined by the Department of Imaging, with the support of [name]. The Doppler transducer will be placed in the neck and the common carotid artery will be located, then the thickness of the intimal vascular mean will be determined 1 cm from the carotid bifurcation. The determination will be made by two observers to estimate the inter-observer correlation. Place: Department of Imaging, CMN "November 20", ISSSTE.

The determination of these variables of cardiovascular risk modification will be determined basally and periodically at 3, 6 and 9 months after bariatric surgery, in all groups.

Definition of the processing plan and presentation of the information

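### Carotid thickness is measured at every visit without masking, and the two-observer correlation cannot detect a shift that both observers share, so the before-after carotid change is open to expectation bias.

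*Combined protocol and SAP*

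**What the plan says.** The paragraph on subclinical atherogenesis, in the section on sources, methods and procedures, assigns carotid intima media thickness to the imaging department: "It will be determined by the Department of Imaging". The measurement is made on the patient: "The Doppler transducer will be placed in the neck and the common carotid artery will be located". A second observer is added for one stated purpose: "The determination will be made by two observers to estimate the inter-observer correlation".

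Carotid thickness belongs to the set introduced with the words "follow-up variables related to post-surgical modification of cardiovascular risk will be determined". That set "will be determined basally and periodically at 3, 6 and 9 months after bariatric surgery, in all groups". The section defining the control group makes each obese patient's pre-surgical value the reference for the later values.

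The same department supports the fat measurements, which are "determined non-invasively by computed tomography, with the support of the Department of Imaging". The table of variables puts body fat on the dependent side and carotid thickness on the independent side. The Design section explains that the labels are deliberately arranged this way: "the independent variable is the change in cardiovascular risk after bariatric surgery". In substance, carotid thickness is a follow-up outcome.

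No section mentions masking of observers, coded or stored images, reading order, or independence of the two readings. The processing plan has no step for reader effects.

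**The concern.** Carotid thickness depends on the observer, and the use of two observers acknowledges this. The measurement is repeated before and after an operation that is expected to help. An observer who knows or can guess that a scan is post-operative may read it slightly thinner without intending to. If both observers do so, they still agree, and the plan's only check reports good reliability.

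What is at stake is the second specific objective, the change in cardiovascular prognosis after surgery, as far as it rests on carotid thickness. Each patient is his own reference, so a shift at post-operative visits enters directly into the estimated change.

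**Working it through.** **Inputs**
- Sample size, from the Design section: p = 0.20, d = 0.13, z = 1.96.
- Two-sided 5% significance, from the processing plan and the sample-size section.
- Reader shift: not in the documents. Assumed values are 0.25 and 0.5, in SDs of the within-patient carotid change.
- Assumed for the illustration: all 37 patients have a baseline and the follow-up reading being tested, there is no true change, and a paired t test is used. The plan names only a difference of averages.

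**Step 1: the plan's own figure.** n = z² p(1 − p)/d² = 3.8416 × 0.16/0.0169 = 0.6147/0.0169 = 36.37. With the plan's rounding, 0.614/0.0169 = 36.33. The stated 36.3 reproduces; rounded up, it is 37 patients.

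**Step 2: where reader bias goes.** Write patient i's reading at visit t as

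Y = truth + b(t) + c·fat(i) + g(t)·fat(i) + error.

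The change from baseline is then

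true change + [b(1) − b(0)] + [g(1) − g(0)]·fat(i) + error.

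- A visit-only shift, b(1) − b(0), biases the mean change.
- A fat-only expectation that acts equally at every visit, c, cancels.
- Only a bias that varies by both fat and visit, g(1) − g(0), makes change depend on fat.

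**Step 3: false change from a uniform post-operative shift.** The paired t test has 36 degrees of freedom, critical value 2.028 and noncentrality δ√37.

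| Shift δ (SD of change) | Noncentrality | Falsely significant |
|---|---|---|
| 0.25 | 1.521 | 31.6% |
| 0.50 | 3.041 | 84.1% |

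A simulation (20,000 replicates) gave 4.8% with no shift, 31% at 0.25 SD and 84% at 0.5 SD.

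**Step 4: effect on the link with fat.** In the same simulation, a uniform shift left the false-positive rate for the correlation between carotid change and fat at about 5% (4.6% at 0.25 SD, 5.0% at 0.5 SD). Only a visit-by-fat bias raises it:
- If post-operative readings differ by 0.25 or 0.5 SD between high-fat and low-fat halves (18 v 19), noncentrality is δ√(18 × 19/37) = 0.760 or 1.520 on 35 degrees of freedom. The false-positive rate is 11.5% or 31.5%.
- If the bias is 0.25 or 0.5 SD per SD of continuous fat, the simulated rate is about 31% or 81%.

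These two lines assume the interaction; they are not evidence that it exists.

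**Step 5: can the two-observer check see it?** Take true values with variance 1 and independent reading errors with SD 0.5 (variance 0.25).
- No bias: correlation = 1/(1 + 0.25) = 0.80.
- Shared uniform shift: still 0.80, because a constant does not enter a correlation.
- Shared bias of 0.5 per SD of fat: (1 + 0.25)/(1 + 0.25 + 0.25) = 0.83.

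The correlation stays the same or rises, so the check cannot flag a shared bias.

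**The case against.** The strongest reply is that the documents do not say what the observers know. Silence on masking is a gap in description, and the plan does not say how the thickness is marked or read. This stands, so the point is about what could happen. Even so, the transducer is placed on a patient who is either awaiting surgery or some months past it, and nothing in the plan keeps that from the observer.

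A reader might also infer that, because one department handles both CT fat and carotid scans, observers could create the association that the study is designed to test. The documents do not support that reading:
- The overlap is shown only at department level. Nothing says that the same people do both tasks or that carotid observers see CT results.
- An expectation tied to fat alone cancels in the within-patient change. A false link needs bias that differs by both fat and visit. Sight of the CT result or of the patient's body size could supply it, but this is conjecture.
- The hypothesis concerns basic mechanisms of adipose tissue. The variable table lists body fat among the dependent variables, but the list of analyses for each metabolic profile covers adipose tissue, liver and serum without CT fat. At most one pairing among several is exposed.

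It is also fair to say that carotid thickness is only one risk measure. Prognostic scales, endothelial markers and the ankle/arm index are also planned, and flow mediated dilatation is in the variable table. Finally, the bias sizes are assumed, and masked reading does not mask acquisition. All of this limits the size of the point. None of it makes the two-observer correlation a substitute for masking.

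**Conclusion.** The point holds for the before-after carotid change. The measurement depends on the observer, is repeated across surgery without masking to visit or group, and is checked only by a statistic that is blind to a shared shift. With 37 patients, no true change and an assumed shift of 0.25 to 0.5 SD of the change, a paired test would be falsely significant in about 32% to 84% of studies, against a nominal 5%. These figures rest on assumed shifts and full follow-up; they show sensitivity and do not estimate the bias in this study.

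The point does not extend to the association with the baseline profile, except under a visit-by-fat bias that the documents do not show. It concerns one risk measure and does not undermine the study as a whole. It is worth acting on because the remedy is cheap and must be in place before scanning: images that were not stored cannot be read masked later.

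**What to change.** In the paragraph on subclinical atherogenesis, state that carotid images from every visit are stored under a code. After the 9-month visit, the same two observers independently read all of a participant's images in random order, masked to visit date, group, CT fat, and tissue or serum results.

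This needs no extra scan, reader or patient, and no change to the sample size. The costs are image storage and coding, and carotid results are not available until the 9-month scans are done. Acquisition stays unmasked, so the choice of site and frame on the day remains open to expectation; the change reduces the problem but does not remove it.

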Patients with morbid obesity subjected to bariatric surgery, with significant modification of cardiovascular risk in the postoperative period.

Definition of the control group

Due to the observational design of the before-after evaluation (of bariatric surgery), the morbidly obese patient in the pre-surgical baseline is his own reference ("control") for the postoperative period. It is also considered non-obese subjects subjected to abdominal surgery eg. Hernioplasty, fundoplication etc. to know the "normal" metabolic profile of adipose tissue.

Inclusion criteria

- Men and women.
- Over 18 years.
- With morbid obesity and candidates for bariatric surgery, under the routine of the treating service.
- Signature of acceptance of your participation, through informed consent.

Exclusion criteria.

- Medication with potential effect on fatty tissue or cardiovascular risk in the last month.
- Serious infections in the last month.
- Clinically unstable conditions.

Elimination criteria.

- Desire not to continue in the study
- Samples or insufficient information for an adequate analysis.

Definition of variables and units of measurement.

Definition of variables and units of measurement.			
Variable	Dependent / Independent	Type	Units of measurement
Total body fat, visceral and subcutaneous	Dependent	Discontinuous Quantitative	Percentage
Serum markers of inflammation PCR and IL-6	Dependent	Quantitative continuous	µUI / dL
Serum adipokines: leptin and adiponectin	Dependent	Quantitative continuous	µUI / dL
Differentiation and hypertrophy of adipocytes and angiogenesis	Dependent	Qualitative dichotomous	Present or absent
Pro-inflammatory markers at tissue level	Dependent	Qualitative dichotomous	Present or absent
Oxidative stress and tissue endoplasmic reticulum	Dependent	Qualitative dichotomous	Present or absent
Insulin sensitivity	Dependent	Qualitative dichotomous	Sensitive or not sensitive
HOMA	Dependent	Qualitative dichotomous	Higher or lower than 15
Prognostic scales mortality due to independent cardiovascular cause	Independent	Quantitative discontinuous	Own rating
Flow mediated dilatation	Independent	Quantitative discontinuous	Percentage
Carotid intima media thickness	Independent	Quantitative discontinuous	Millimeters

Selection of sources, methods, techniques and procedures for collecting information

With the acceptance of the Institutional Ethics, Research and Biosafety Committees, patients will be invited and included according to the selection criteria.

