Data analysis will be done through descriptive statistics applied to demographic variables, and inferential statistics, which will include difference of averages, correlation, strength of association and relative risk, as well as multivariate logistic regression analysis to evaluate independent associations. With the variables most associated with the modification of cardiovascular risk, a metabolic profile will be established as a predictive model of the greatest cardiovascular benefit after bariatric surgery. Statistical significance will be considered with $p < 0.05$

ETHICAL CONSIDERATIONS

This study is considered as minimal risk. Bariatric surgery (this procedure is not a proposal of the present protocol, it is routinely done as a treatment for morbid obesity in the CMN "20 de Noviembre", ISSSTE and would also be done if the patient does not participate in the study) will be performed according to the routine procedures of the Department of Bariatric Surgery. The project complies with the guidelines and recommendation of the Declaration of Helsinki. The protocol will be submitted to the Ethics and Institutional Research Committee. All patients will be asked to read and sign informed consent.

BIOSECURITY CONSIDERATIONS.

Bariatric surgery procedures are not part of this investigation. In any case, it is emphasized that this project does not alter the surgical procedure and routine biosecurity measures, which are based on the best clinical practice and international recommendations (Neff KJ, le Roux CW, Bariatric surgery: a best practice article. *Pathol* 2013; 66: 90-8). Sampling during surgery will be done in accordance with the Regulation of the General Health Law on Health Research, respecting aspects of taking the appropriate measures to avoid any risk or damage to research subjects (includes adequate preoperative assessment). , biosecurity measures typical of an operating room and sampling by an experienced surgeon). In any case, the privacy of the individual subject of the investigation will be protected, and it will be sought to limit the likelihood that the subject will suffer any harm as a result of the study.

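### The regression meant to show independent associations commits to no baseline-risk covariate, so the plan does not assure that a selected adipose marker predicts benefit beyond starting risk

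*Combined protocol and SAP*

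**What the plan says.** The section on the processing plan and presentation of the information is the whole analysis plan. Its group comparisons are described as "inferential statistics, which will include difference of averages, correlation, strength of association and relative risk". For adjusted work it offers a single regression, introduced by the words "as well as multivariate logistic regression analysis to evaluate independent associations". The profile is then derived in this way: "With the variables most associated with the modification of cardiovascular risk, a metabolic profile will be established as a predictive model". What that model should predict is who gains most from the operation. No covariate of any kind is named.

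The third specific objective is to "Determine the association of the cardiovascular prognosis modification (risk subgroups) with the basal metabolic profile". The design section labels the change in risk as the independent variable and the adipose profile as the dependent one, adding that "This order of variables was decided by methodological strategy".

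The variables table contains dichotomous tissue markers (for example "Pro-inflammatory markers at tissue level", present or absent) and continuous serum markers ("Serum adipokines: leptin and adiponectin").

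Risk is scored "using Framingham or SCORE scales". The scores and the other risk measures are taken at baseline and at 3, 6 and 9 months, so the baseline value will be in the data set.

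**The concern.** Change in risk is computed from the starting value, so it is usually correlated with it. When patients who start higher also fall further, any marker that follows starting risk is associated with the size of the fall, even if it says nothing about follow-up risk once the baseline score is known. The mean differences, correlations and relative risks in the plan carry no baseline term, and the regression does not promise one. Using each patient as his or her own control yields a change; it does not adjust for where the patient started.

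At stake is the interpretation of the study's main product. A reader could not tell a tissue profile that adds information from one that repeats a risk score available without a biopsy.

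**Working it through.** **The plan's own figure.** n = 1.96² × 0.20 × 0.80 / 0.13² = 0.6147 / 0.0169 = 36.37. The plan states 36.3, so the figure reproduces; rounded up it is 37. This is a precision formula for one proportion and does not size a regression. The smaller outcome group would hold about 37 × 0.20 = 7.4 patients if the 20% prevalence is read as the outcome rate, or 37 × 0.50 = 18.5 under a median split. Both readings are assumptions.

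**Inputs for the check.** From the documents: n = 37, p < 0.05 (taken as two-sided), present/absent and continuous markers, risk subgroups. Assumed: absolute change, slope of follow-up on baseline risk, marker-baseline correlation ρ, residual SD, marker prevalence of 20% or 50%, and a median split of the fall in risk. Baseline SD is set to 1. The marker carries no information once baseline is known.

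**Closed form.** With follow-up = slope × baseline + error, the correlation between marker and fall in risk is

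ρ(1 − slope) / √[(1 − slope)² + residual variance].

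- Slope 0.8, ρ = 0.3, equal variances (residual variance 1 − 0.64 = 0.36): 0.06 / √0.40 = 0.095.
- Slope 0.5, ρ = 0.5, equal variances (residual variance 0.75): 0.25 / √1.00 = 0.25.
- Slope 0.5, ρ = 0.5, residual SD 0.5: 0.25 / √0.50 = 0.354.
- Slope 1: 0 for any ρ.

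For a continuous marker and continuous change, Fisher's z with n = 37 gives atanh(0.25) × √34 = 1.49, so the chance of significance is Φ(1.49 − 1.96) ≈ 32%. For 0.354 it is Φ(2.16 − 1.96) ≈ 58%. Simulation of 20,000 runs per setting agrees (32.4% and 59.3%).

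**The analysis closest to the plan's words.** This is a present/absent marker against median-split subgroups, with the logistic likelihood-ratio test used both with and without baseline:

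| Assumed setting | Without baseline | With baseline |
|---|---|---|
| Slope 0.8, ρ = 0.3, equal variances | 6.3–7.8% | 6.2–7.4% |
| Slope 0.5, ρ = 0.5, equal variances | 14–15% | 6–8% |
| All settings, slopes 0.5–0.8, ρ 0.3–0.5 | about 7–27% | about 5–7% |

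The 27% comes from slope 0.5, ρ = 0.5 and residual SD 0.5. At slope 1 the unadjusted chi-square test stays at 4.8–5.5%.

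**Where adjustment can mislead.** At slope 1 with an assumed baseline reliability of 0.8, the adjusted logistic test flags the same empty marker in about 6% to 11% of runs, while the unadjusted test stays near 5%.

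**The case against.** The strongest reply is that the plan rules nothing out. The regression is multivariable, its declared purpose is independence, baseline risk is collected, and no covariate at all is named, so baseline risk has not been singled out for omission. The plan also does not say independent of what; mutual independence among the adipose variables would fit the words. This stands against two stronger readings that a reader might infer:

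- That the plan is unable to show independence from starting risk. The documents do not support this: baseline risk is neither named nor excluded, and an analyst could enter it.
- That a baseline-tracking marker would be a false positive for the study hypothesis. H0, the general objective and the third specific objective ask only about association, and an unadjusted association with change can be real.

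A second reply is that the size is wholly assumed. This also stands. At slope 0.8 and correlation 0.3 adjustment gains almost nothing for a dichotomous marker, and at slope 1 nothing. The figures near 59% need a continuous marker, continuous change and the most favourable slope, correlation and residual SD, so they should not be read as typical.

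A third reply is that the undefined outcome is the more basic gap: the choice of scale, absolute or relative change, and the subgroup cut-points are all open. That is fair, but it is a separate matter of missing detail. Whatever outcome is chosen, its baseline value will be available. What none of these replies removes is that variables are selected on association with change, with no commitment to the one covariate that is arithmetically tied to change.

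**Conclusion.** The point holds as a gap in commitment. Nothing in the plan assures that a marker selected into the profile predicts benefit beyond the risk known before surgery. The absence of a named covariate is certain; the consequence is conditional. It requires absolute change, a slope below 1 and a marker correlated with baseline risk. Under the assumed ranges, the chance of selecting an uninformative present/absent marker moves from about 5–7% with baseline in the model to about 7–27% without it, the lower end being no real difference. The remedy is worth making because the data are already collected and the wording is short. Confidence is medium, because slope, correlation, residual SD and prevalence are not in the documents.

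**What to change.** Add to the processing-plan section: *Each candidate adipose variable is tested with the baseline value of the same risk measure as a covariate. Unadjusted and baseline-adjusted associations are reported side by side. A variable is called an independent predictor of benefit only if its association remains after baseline adjustment.*

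Reporting disagreement between the two results as inconclusive is optional. It guards against distortion from a noisy baseline but costs power. With a real marker at 50% prevalence and an effect of 0.5 baseline SD (assumed), slope 0.5 and no correlation with baseline, power is 38% unadjusted, 54% adjusted and 35% if both must agree.

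Costs:

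- Visits, outcomes and the logistic model are unchanged. The variable order in the design section can stay: with the marker as the dependent variable, the adjusted verdict matched the reverse order in 96% to 99.6% of simulated runs.
- A single-marker model loses one degree of freedom. At slope 1 and correlation 0.5, power for the same real marker falls from 64% to 58%.
- With about 7 to 18 patients in the smaller outcome group, a multi-marker profile has less room once baseline is included. With three uninformative markers tested jointly, the adjusted model rejected in 6% to 10% of runs, so the profile should be kept small.
- If baseline is measured with error and the slope is near 1, adjustment can itself create an association. Side-by-side reporting makes this visible.

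### With about 37 patients and perhaps 7 in the smaller outcome class, the planned logistic regression has no small-sample method and does not give a 5% test, even with markers fixed in advance

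*Combined protocol and SAP*

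**What the plan says.** The section on the processing plan and presentation of the information lists descriptive statistics, differences of averages, correlation, strength of association and relative risk. It then adds "multivariate logistic regression analysis to evaluate independent associations". The variables most associated with the change in cardiovascular risk are to form a profile that predicts the greatest benefit after surgery. "Statistical significance will be considered with" p < 0.05. The section does not define the binary outcome or its cut-off, the number of covariates, the test (Wald or likelihood-ratio) or any small-sample method.

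The DESIGN section sizes the obese cohort with a single-proportion precision formula. Z is the "value of the alpha error with a confidence of 95%, assigning alpha = 0.05", p is the "Expected population prevalence for the event under study (according to previous reports" and set at 0.20, and d is 0.13. The result is 36.3. The event is not named. A further "10 non-obese patients undergoing non-bariatric surgery" serve for comparison. Patients are to be stratified by change in cardiovascular risk, with no cut-off given.

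The variables table has eight rows labelled dependent. Five are dichotomous: insulin sensitivity, HOMA and three present/absent tissue rows, such as "Pro-inflammatory markers at tissue level". The three rows labelled independent (prognostic scales, flow-mediated dilatation, carotid intima-media thickness) are all quantitative.

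**The concern.** Logistic regression by maximum likelihood relies on large-sample theory, and the information it has is set mainly by the smaller outcome class. With very few events, three things can go wrong. Estimates of real associations move away from 1. Tests miss their nominal level. A binary marker may be present only, or absent only, in one outcome class (separation), so that no finite odds ratio exists.

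This differs from the optimism that comes from picking the most associated markers. It is a failure of estimation that remains when every marker is named beforehand, and later validation would not repair it. At stake is the third specific objective, the association between change in cardiovascular prognosis and baseline profile, together with the predictive profile built on it.

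**Working it through.** **1. The plan's own figure.** n = Z²p(1−p)/d² = 1.96² × 0.20 × 0.80 / 0.13² = 0.6147 / 0.0169 = 36.37. The stated 36.3 reproduces, so the cohort is 36 or 37 patients. The formula contains no power, effect size, covariate count or allowance for dropout.

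**2. Events.** If 0.20 is the benefit proportion, 36 × 0.20 = 7.2 and 37 × 0.20 = 7.4, so about 7 (95% binomial range 3 to 12). The comparison patients have no bariatric surgery and add none. Events per marker: 7/2 = 3.5 with two markers and 7/8 = 0.9 with eight. An even split gives about 18 in the smaller class: 18/2 = 9 and 18/8 = 2.3.

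**3. Size of the tests.** These are simulations with 37 patients, uncorrelated markers fixed in advance, no selection, binary markers present in 30%, and the tested marker having no effect. Non-finite fits count as non-rejections for Wald. With 2,500 data sets the Monte Carlo standard error of a 5% rate is √(0.05 × 0.95/2,500) = 0.4 points. Figures are approximate rejection rates at nominal 5%.

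| Smaller class | Markers in model | Likelihood-ratio | Wald | No finite estimate |
|---|---|---|---|---|
| 7 | 2 continuous | 6% | 4% | none |
| 7 | 2-3, at least one binary | 9% | 2% | 10-15% |
| 7 | 8 (4 continuous, 4 binary) | 14% | 1% | 30% |
| 18 | 2-3 | 5-7% | 4-5% | almost none |
| 18 | 8 | 10% | 6.5% | 1.4% |

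Separate runs move these figures by a point or two. For one continuous and two binary markers at 7 events, for example, the likelihood-ratio rate lay between 7.5% and 9.7%. With the variables table's own mix of three continuous and five binary rows, separation is 35% and the likelihood-ratio rate 13-14%.

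**4. Size of the odds ratios.** With a true odds ratio of 2 per SD, a 20% event rate and continuous markers, the median estimate is 2.1 with two markers (geometric mean 2.42) and about 2.4 with five (geometric mean 2.96). With eight markers, exactly 7 events and binary markers at 50%, the median is 2.9 where an estimate exists, and 13% of data sets have none. With no true association there is no directional bias.

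**5. Alternatives.** Firth regression with a penalised-likelihood test rejected 3.6-5.7% across the settings, and can be somewhat conservative for a sparse binary marker. With two to five markers it recovered a true odds ratio of 2 as 1.94-2.13 (geometric mean). Its power for that odds ratio is only 28-29% for a continuous marker and 11-12% for a binary one. Linear regression of a continuous outcome rejected 4.9% and cannot suffer separation.

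**The case against.** The strongest reply is that the plan does not fix the conditions under which the failure is severe. Most of this stands.

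- **Seven events is not the plan's figure.** The event behind 0.20 is never named, and the explanation of d refers to mechanisms in adipose tissue. No cut-off for change in risk is given, so a median split is equally open. With about 18 in the smaller class and two or three markers, little is left of the problem. Still, 0.20 is the only event rate in the document.
- **Eight markers in one model is not stated.** A reader might infer it from the variables table, but no section says so. The eight-marker results are an upper case.
- **A reader might infer that false positives are bound to be too many.** That is true only of the likelihood-ratio test. At 7 events Wald errs the other way and would hide real markers. Since the plan names neither, the error rate is left to a software choice.
- **A reader might infer that every odds ratio will be exaggerated.** Inflation needs a true association, and is modest with two continuous markers. With binary markers the main trouble is separation.

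The plan also lists correlation and differences of averages, which can use the quantitative risk measures. Neither adjusts markers for one another, so they do not replace the analysis of independent associations.

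**Conclusion.** The concern holds conditionally. If about 7 of 37 patients form the smaller class, the planned regression does not deliver its stated 5% level, even with markers named in advance. The error is slight with two continuous markers. It is material once a binary marker enters: about 9% by likelihood-ratio, about 2% by Wald, and 10-15% of data sets without a finite estimate. It is severe with eight. Under an even split it is small with two or three markers and persists with eight.

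This rests on three assumptions: that 0.20 is the benefit proportion, that binary markers are present in 30%, and that ordinary maximum likelihood is meant, since no other method is mentioned. The document does not support saying that the study will have 7 events, that eight markers will be fitted together, or that the analysis will necessarily produce excess false positives. A change is nevertheless advisable, because the analysis section rules out none of the bad cases and the remedy costs little.

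**What to change.** In the processing-plan section, make the main multivariable analysis a linear regression of the quantitative change in cardiovascular risk (score points, or mm for carotid thickness) on a small set of baseline markers named in advance. State the risk measure and the visit. Add that this reverses the dependent and independent labels in the DESIGN section and the variables table, but agrees with the processing plan's aim of predicting benefit.

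If a yes/no benefit outcome is kept, define its cut-off and fit it by Firth penalised logistic regression, with penalised-likelihood tests and profile intervals. Report the remaining markers one at a time as exploratory. The exact cap on marker terms is a matter of judgement; these calculations do not yield a particular number.

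The cost is plan wording only, and the methods are in standard software. The downsides are that fewer markers are mutually adjusted in one model, and that penalisation corrects bias and test size but not low power.
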